7. STUDY IMAGING PROCEDURES

7.1 Sequence of Imaging and Standard SBRT Work-up and Treatment

	Pre-Registration	Day -14 to 0	Day 1-15	Day 8-29 (1-2 wks post SBRT)	Day 90-120
Study DCE-MRI		X	X	X	X
MRI Screening	X		X	X	X
Study 4D-CT					X
Timing of Standard Treatments and Work-up					
SBRT Treatments			X		
PET-CT	X				X
PFT	X				X
Blood Tests	X		X	X	X
History	X			X	X
Physical Exam	X			X	X

7.2 Description of Pulmonary DCE-MRI Imaging

CONFIDENTIAL

This document is confidential. Do not disclose or use except as authorized.

Participants will undergo pulmonary DCE-MRI at baseline before the stereotactic body radiation therapy, during treatment (1-2 days after the first SBRT fraction) and post-treatment (1-2 weeks and then 3-4 months). Pulmonary DCE-MRI scans will be performed per the standard protocol of the Brigham and Women's Hospital's Department of Radiology. MR images will be obtained following the intravenous bolus injection of 0.1 mM/kg of body weight of gadolinium at the rate of 3 milliliters (mL)/second, followed by 20 mL of saline at the rate of 3 mL/second. Each scan is approximately 60 minutes.

The devices and software that will be used for DCE-MRI have FDA (510K) approval and are commercially available.

Time to peak perfusion signal and enhancement ratio (defined as post- to pre-contrast perfusion signal) at the time of maximal parenchymal enhancement (TMPE) will be measured on each DCE-MRI scan. Pharmacokinetic parameters, including the volume transfer constant (K_{trans}), the fractional volume of extravascular extracellular space of the target tissue (v_e), and the rate constant (k_{ep}), will be estimated by fitting a pharmacokinetic model to the actual time-intensity curves obtained from the DCE-MRI.

We will adopt the generalized kinetic model (Tofts, Brix et al. 1999), which is described as follows

$$dC_t / dt = K^{trans} (C_p - C_t / v_e) - k_{ep} C_t$$

where C_t : tracer concentration in tissue, C_p : tracer concentration in arterial blood plasma, K^{trans} : transfer constant, v_e : extravascular extracellular space fraction volume, k_{ep} : rate constant.

The solution to the above mentioned equation with the initial condition that $C_p = C_t = 0$ at $t=0$, is

$$C_t(t) = K^{trans} \int C_p(\tau) \exp(-k_{ep}(t-\tau)) d\tau$$

The tissue response to a short arterial pulse of concentration = 1/ (pulse duration), i.e., a delta function, is

$$h(t) = K^{trans} \exp(-k_{ep} t)$$

Thus K^{trans} determines the amplitude of the initial response (the amount of tracer entering the extravascular extracellular space), and k_{ep} determines the washout rate from the extravascular extracellular space back into the blood plasma.

The mean residence time is then:

$$\tau = \int_0^{\infty} t h(t) dt / \int_0^{\infty} h(t) dt$$

CONFIDENTIAL

This document is confidential. Do not disclose or use except as authorized.

The response to a step change in arterial plasma concentration, from 0 to C_p , at time $t=0$, is

$$C_t(t) = K^{\text{trans}} C_{p0} / k_{ep} (1 - \exp(-k_{ep} t)) = v_e C_{p0} (1 - \exp(-k_{ep} t))$$

The response to a step change from C_{p0} to zero is

$$C_t(t) = K^{\text{trans}} C_{p0} / k_{ep} \exp(-k_{ep} t) = v_e C_{p0} \exp(-k_{ep} t)$$

During the analysis, intra-tumor heterogeneity will be corrected for using the recently published method of pixel-wise pharmacokinetic analysis for DCE-MRI of the lung, utilizing pixel-by pixel fitting (Tokuda, Mamata et al. 2011).

Pulmonary DCE MRI scans will be performed at the following time points:

- 7.2.1 Pre-treatment: The first pulmonary DCE-MRI will be performed within 2 weeks prior to the start of SBRT. Protocol DCE-MRI must begin within 4 weeks of registration.
- 7.2.2 During SBRT MRI: 1-2 days after the first SBRT treatment (Day 2-3)
- 7.2.3 Early post-SBRT MRI: 1-2 weeks after completion of SBRT
- 7.2.4 Late post-SBRT MRI: 3-4 months after completion of SBRT

7.3 DCE-MRI Adverse Events

As this study involves pulmonary DCE-MRI with gadolinium contrast, which is a FDA approved procedure, severe adverse reactions related to the study imaging would not be expected to occur. Any adverse events that do occur will be reported to the IRB and the patient's primary radiation oncologist. See Appendix C for Adverse Event Reporting Guidelines.

7.3.1 DCE-MRI Anticipated reactions

As a consequence of participation in the study, participants may experience frustration or anxiety related to time spent obtaining the additional study MRI scans. Participants would also be at risk of the typical reactions from MRI with gadolinium contrast administration:

Occasional (occurring in 2 or 3 out of 100 patients):

- Mild nausea (with or without vomiting), tingling sensation, headache, dizziness, coldness at the injection site, headache, warmth or pain at the injection site, paresthesias, dizziness, and itching

Rare (occurring in 1 patient or less out of 100):

- Severe anaphylactic reaction

CONFIDENTIAL

This document is confidential. Do not disclose or use except as authorized.

- Severe Nephrogenic Systemic Fibrosis (NSF) in patients with chronic renal insufficiency

7.4 Description of Study 4D-CT

4D-CT scanning will be performed per standard protocol in the Brigham and Women's Hospital's Department of Radiation Oncology. 4D-CT is an FDA-approved imaging technique in which a longer-duration CT scan is acquired that accounts for the breathing motion of the patient. In anatomic regions where motion is present (e.g., the lung), 4D-CT is better for determining the tumor volume (Keall, Starkschall et al. 2004) than conventional CT which is insensitive to periodic motion. Each scan is approximately 15 minutes in duration.

The devices and software that will be used for 4D-CT have FDA (510K) approval and are commercially available.

Participants receive an additional radiation dose of 30 mSv-50 mSv (Murphy et al. 2007) when subjected to a 4D-CT scan. This dose is equivalent to 5-8 times the annual radiation dose to the general public (National Council on Radiation Protection and Measurements., National Council on Radiation Protection and Measurements. Scientific Committee 6-2 on Radiation Exposure of the U.S. Population. et al. 2009) and is not associated with deterministic effects of radiation.

7.5 4D-CT Adverse Events and Anticipated Reactions

As a consequence of participation in the study, participants may experience frustration or anxiety related to time spent obtaining the additional study 4D-CT scan. Additional adverse events due to 4D-CT are extremely rare but potentially severe:

Extremely Rare (occurring in 1 patient or less out of 1000)

- Radiation-induced tumors

8. RADIATION THERAPY

8.1 Radiotherapy: Stereotactic Body Radiation Therapy (SBRT)

All SBRT treatment planning, plan evaluation and treatment delivery will be conducted per the standard of care, and there is no investigational aspect to the radiotherapy delivered to participants on this study. The following description is for guidance but the treating radiation oncologist may alter the plan if circumstances warrant after discussion with the Principal Investigator.

8.2 Dose Specifications: Stereotactic Body Radiation Therapy (SBRT)

CONFIDENTIAL

This document is confidential. Do not disclose or use except as authorized.

- 8.2.1 Dose will be normalized such that 95% of the PTV receives the prescription dose as per normal treatment protocol. The minimum allowable dose within the PTV is >95% of the prescribed dose.
- 8.2.2 Patients shall receive prescription doses to the PTV (with the above constraints). All attempts should be made to deliver the PTV dose with the above heterogeneity constraints with adherence to the critical structure parameters listed below in Table 1. See Section 8.6 below for specifics regarding when to implement a dose reduction. The final prescription dose will be recorded on a patient-by-patient basis.
- 8.2.3 The treating radiation oncologist will use our standard risk-adapted SBRT treatment approach to select the prescription dose. If critical-structure dose constraints are met (see Table 1), then the standard dose prescription would be 54 Gray in 3 fractions. However, if dose constraints to critical organs such as the bronchial tree and chest wall cannot be met at this dose prescription, than the treating radiation oncologist may chose to deliver the treatment over 5 fractions with a dose of 10 to 12 Gray.

Table 1. Critical-Structure Dose Constraints

Constraints for 3 Fractions

Serial Tissue	Volume	Volume Max (Gy)	Max Point Dose (Gy)
Spinal cord and medulla	<0.35 cc <1.2 cc	18 Gy (6 Gy/fx) 12.3 Gy (4.1 Gy/fx)	21.9 Gy (7.3 Gy/fx)
Spinal cord subvolume (5-6 mm above and below level treated per Ryu)	<10% of subvolume	18 Gy (6 Gy/fx)	21.9 Gy (7.3 Gy/fx)
Esophagus*	<5 cc	17.7 Gy (5.9 Gy/fx)	25.2 Gy (8.4 Gy/fx)
Brachial plexus	<3 cc	20.4 Gy (6.8 Gy/fx)	24 Gy (8 Gy/fx)
Heart/pericardium	<15 cc	24 Gy (8 Gy/fx)	30 Gy (10 Gy/fx)
Great vessels	<10 cc	39 Gy (13 Gy/fx)	45 Gy (15 Gy/fx)
Trachea and large bronchus*	<4 cc	15 Gy (5 Gy/fx)	30 Gy (10 Gy/fx)
Bronchus-smaller airways	<0.5 cc	18.9 Gy (6.3 Gy/fx)	23.1 Gy (7.7 Gy/fx)
Rib	<1 cc	28.8 Gy (9.6 Gy/fx)	36.9 Gy (12.3 Gy/fx)
Skin	<10 cc	30 Gy (10 Gy/fx)	33 Gy (11 Gy/fx)
Parallel Tissue	Critical Volume (cc)	Critical Volume Dose Max (Gy)	
Lung (Right & Left)	1500 cc	10.5 Gy (3.5 Gy/fx)	
Lung (Right & Left)	1000 cc	11.4 Gy (3.8 Gy/fx)	
Liver	700 cc	17.1 Gy (5.7 Gy/fx)	

*Avoid circumferential irradiation

Constraints for 5 Fractions

Serial Tissue	Volume	Volume Max (Gy)	Max Point Dose (Gy)
Spinal cord and medulla	<0.35 cc <1.2 cc	23 Gy (4.6 Gy/fx) 14.5 Gy (2.9 Gy/fx)	30 Gy (6 Gy/fx)
Spinal cord subvolume (5-	<10% of	23 Gy (4.6 Gy/fx)	30 Gy (6 Gy/fx)

CONFIDENTIAL

This document is confidential. Do not disclose or use except as authorized.

6 mm above and below level treated per Ryu)	subvolume		
Esophagus*	<5 cc	19.5 Gy (3.9 Gy/fx)	35 Gy (7 Gy/fx)
Brachial plexus	<3 cc	27 Gy (5.4 Gy/fx)	30.5 Gy (6.1 Gy/fx)
Heart/pericardium	<15 cc	32 Gy (6.4 Gy/fx)	38 Gy (7.6 Gy/fx)
Great vessels	<10 cc	47 Gy (9.4 Gy/fx)	53 Gy (10.6 Gy/fx)
Trachea and large bronchus*	<4 cc	16.5 Gy (3.3 Gy/fx)	40 Gy (8 Gy/fx)
Bronchus-smaller airways	<0.5 cc	21 Gy (4.2 Gy/fx)	33 Gy (6.6 Gy/fx)
Rib	<1 cc	35 Gy (7 Gy/fx)	43 Gy (8.6 Gy/fx)
Skin	<10 cc	36.5 Gy (7.3 Gy/fx)	39.5 Gy (7.9 Gy/fx)
Parallel Tissue	Critical Volume (cc)	Critical Volume Dose Max (Gy)	
Lung (Right & Left)	1500 cc	12.5 Gy (2.5 Gy/fx)	
Lung (Right & Left)	1000 cc	13.5 Gy (2.7 Gy/fx)	
Liver	700 cc	21 Gy (4.2 Gy/fx)	

*Avoid circumferential irradiation

Constraints for 3 or 5 Fractions

Serial Tissue	Dose-Volume Histogram Parameter	Constraint
Lung (Right & Left)	V20	<10%
Lung (Right & Left)	V10	<12%
Lung (Right & Left)	Mean lung dose	4 Gray
Chest wall	V30	< 30 cc

8.3 Technical Factors: Stereotactic Body Radiation Therapy (SBRT)

- 8.3.1 SBRT will be delivered with linear accelerators at energies ≥ 6 MV.
- 8.3.2 SBRT immobilization, simulation, planning, localization, and image-guidance will be utilized in all participants per standard clinical care as described below.
- 8.3.3 SBRT may be delivered using 3D-conformal or volumetric modulated arc therapy (VMAT) techniques per standard clinical care as described below.

8.4 SBRT Localization, Simulation, and Immobilization

Participants will be simulated using four-dimensional computed tomography (4DCT), which incorporates tumor motion into planning. The free-breathing scan will be performed with 2.5 mm slice thickness, and the use of contrast at the time of simulation is preferred if feasible, which is our departmental standard protocol for lung simulations. Patients will be simulated in the Elekta Stereotactic frame or similar stereotactic custom immobilization device for stabilization and setup reproducibility. Abdominal compression will be used if the tumor moves more than 1 cm with respiratory motion. Target volumes and normal critical structures will be defined in the

CONFIDENTIAL

This document is confidential. Do not disclose or use except as authorized.

slices in which they are visualized. The 3D conformal cases must utilize “beam’s eye view” representations to define final beam aperture.

8.5 Treatment Planning/Target Volumes

8.5.1 The definition of volumes will be in accordance with the ICRU Report #50: Prescribing, Recording, and Reporting Photon Beam Therapy.

8.5.1.1 The Gross Tumor Volume (GTV) is defined by the physician as all known disease as defined by the planning CT. The internal target volume (ITV) will include the GTV and the movement of the GTV as measured by 4D-CT.

8.5.1.2 The Planning Target Volume (PTV) will provide a margin around the ITV to compensate for the variability of treatment set up and internal organ motion. A margin of 5 mm around the ITV is required to define each respective PTV. Superior and inferior margins (capping) should be 5-10 mm depending on the thickness and spacing of the planning CT scan.

8.5.1.3 The ICRU Reference Points are to be located in the central part of the PTV and, secondly, on or near the central axis of the beams. Typically these points should be located on the beam axes or at the intersection of the beam axes.

8.5.1.4 Normal Critical Structures to be defined on the treatment planning CT scan will include the following: All structures will be contoured in their entirety as solid organs. See the ITC web site (<http://atc.wustl.edu>) to view examples of target and normal tissue contours.

8.5.1.5 The PTV forms the entire target as described. 3D conformal beams will be shaped to include the entire PTV and minimize dose to surrounding critical structures as described. Intensity modulated radiotherapy (IMRT) using inverse planning is permitted with constraints placed to adhere to critical structure dose limitations as defined above.

8.6 Critical Structures

Critical-structure dose constraints shall remain consistent with Table 1 above. While every effort should be made to deliver prescription doses to the PTV as specified while adhering to these constraints, it is recognized that certain anatomical factors may prevent this. A dose reduction should be considered at the discretion of the treating radiation oncologist (for instance, in the case of an increase in critical-structure volume greater than 5% receiving more than the specified dose).

CONFIDENTIAL

This document is confidential. Do not disclose or use except as authorized.

8.7 Treatment Verification

- 8.7.1 Per standard clinical treatment protocols, prior to each SBRT treatment, localization will include initial alignment to infrared markers attached to the stereotactic board. On-line target localization will then be performed first by using kV imaging with the ExacTrac system, and then by cone beam CT. The use of image guidance or daily target localization including the specific type implemented must be documented by the treating physician per normal clinical practice.
- 8.7.2 Management of Radiation Dose to the Patient from Daily Localization

According to the literature, the estimates of patient dose per imaging study for various imaging systems vary considerably. The doses are in the range of 0.1 cGy for BrainLab's ExacTrac planar kV-systems and can be considered negligible compared with doses from MV portal imaging and kV and MV CT. The doses from kV cone beam CT on Elekta Synergy machine are estimated to range from 1 to 3 cGy. Thus, the doses for 3D imaging systems used one time each day are in the range of 0.1 to 10 cGy and can contribute from 0.006 to 0.6% to a daily dose of 18 Gy. As a technique of controlling patient dose, it is recommended that a QA procedure be established at each institution to verify the accuracy of the image registration software on a daily basis. This QA check should be performed by the therapists operating a particular treatment device and is aimed at reducing the use of repeat imaging to check that the registration software has functioned properly when a shift of patient position is carried out. Additionally, it is not recommended that an institution use a daily imaging technique that delivers greater than 3 cGy/day to the patient. This limit dictates that repeat imaging on a particular day is held to a minimum when systems that deliver up to 3 cGy per study are used.

8.8 Quality Assurance

- 8.8.1 Documentation Requirements

The institution will archive treatment prescription and verification images for later review as per standard practice.

8.9 Radiation Quality Assurance Reviews

Since there are no experimental components to radiation therapy on this study, SBRT treatment plans will be subject to standard peer-review and departmental quality assurance reviews per departmental standards. RT quality assurance reviews will be facilitated by the study chair.

8.10 Radiation Adverse Events

- 8.10.1 All participants will be seen at each SBRT treatment and 1 week after treatment by their treating radiation oncologist. Any observations with respect to the following symptoms/side effects will be recorded:

Immediate Reactions

Common:

- Moderate tiredness
- Moderate skin reddening & irritation
- Mild to moderate cough
- Mild to moderate trouble swallowing/sore throat
- Mild decreased blood cell count
- Mild temporary loss of hair in the treated area

Uncommon

- Moderate inflammation of the lung

Rare:

- Mild to moderate nausea

Extremely Rare:

Long Term Reactions

Common:

- Mild scarring of the lung, not requiring treatment
- Mild shortness of breath
- Mild dryness of the skin in the area of treatment

Uncommon

- Moderate scarring or inflammation of the lung requiring treatment
- Mild to moderate inflammation of the heart
- Mild permanent darkening of the skin
- Mild to moderate cough
- Rib fracture causing moderate pain
- Mild to moderate inflammation of the muscle of the chest wall

Rare:

- Severe brachial plexus injury

Extremely Rare:

- Severe swallowing difficulties requiring surgery
- Heart attack (severe)
- Severe nerve damage
- Severe spinal cord injury
- Fatal inflammation or scarring of the lungs
- Tumors caused by radiation

8.10.2 Clinical discretion may be used in managing radiotherapy-related side effects.

8.11 Radiation Adverse Event Reporting

See Appendix B for Adverse Event Reporting Guidelines.

9. DRUG THERAPY

CONFIDENTIAL

This document is confidential. Do not disclose or use except as authorized.

N/A

10. SURGERY

N/A

11. OTHER THERAPIES

As per standard clinical care, participants that require pre-medication for anxiety or claustrophobia prior to MRI may be given lorazepam 0.5-1 mg by mouth (or equivalent medications) prior to the MRI at the discretion of the treating physician. As per standard clinical care, participants will be pre-medicated with a single dose of dexamethasone 4 milligrams by mouth the morning prior to each SBRT treatment. Participants may receive medications for management of potential expected adverse effects secondary to SBRT per standard clinical care.

12. TISSUE/SPECIMEN SUBMISSION

N/A

13. PATIENT ASSESSMENTS

13.1 Schedule of Patient Assessments

See Table of patient assessments in Section 7.1.

13.2 Study Pulmonary DCE-MRI

The participants will undergo a pulmonary DCE-MRI prior to SBRT, during SBRT (1-2 days after the first SBRT treatment) and then two post-treatment DCE-MRI scans, the first within 1-2 weeks after the final treatment and then 3-4 months after SBRT.

13.3 PET-CT and PFT

As part of the standard pre-treatment work-up, participants will undergo a baseline PET-CT and PFT, and then repeat studies 3-4 months after completion of the SBRT treatment. The PFTs will include forced expiratory volume in 1 second (FEV1), forced vital capacity (FVC) and diffusion capacity of the lung for carbon monoxide (DLCO) will be measured.

13.4 Blood Tests

Each participant will have a BUN and creatinine sent within three weeks of each of the four DCE-MRI scans to document eligibility to receive gadolinium contrast based on renal clearance per the eligibility criteria (Section 3.2.4). If the estimated glomerular filtration rate is $< 30 \text{ mL/min/1.73 m}^2$ the participant will not receive gadolinium contrast and will not undergo the scheduled DCE-MRI at that time point and will be re-evaluated

CONFIDENTIAL

This document is confidential. Do not disclose or use except as authorized.

with repeat BUN and creatinine at the next time point. A serum pregnancy test will be obtained in the baseline blood tests if the participant is a female of child-bearing age.

13.5 History and Physical Exam

For the baseline visit, a complete history and physical exam will be done to determine eligibility for the study. At subsequent visits, focused history and physical exams will be performed to assess for side effects of SBRT treatment as per standard care.

14. DATA COLLECTION

14.1 Data Reporting Methods

The QACT will collect, manage, and monitor data for this study. Note: All adverse events that have occurred on the study, including those reported through AdeERS, must be reported via CTMS or CDUS.

14.2 QACT Data Submission

The schedule for completion and submission of case report forms (paper or electronic) to the QACT is as follows:

Form	Submission Timeline
Eligibility Checklist	Complete prior to registration with QACT
On Study Form	Within 21 days of registration
Adverse Event Report Form	Within 14 days of completing last DCE-MRI scan
Off Study Form	Within 21 days of completing last DCE-MRI or being taken off study for any reason

14.3 Study Imaging Data Elements

Pulmonary DCE-MRI and 4D-CT data will be transferred electronically to the [name] and [name] laboratories for analysis of tumor and lung parenchyma perfusion. Additionally, images will be imported into our departmental radiation treatment planning software for further analysis of the utility of the pulmonary DCE-MRI and 4D-CT data for SBRT treatment planning. Images will be identified only by a study ID number. The patient's identifying information (name, MR#, DOB) will be removed before the images are transferred.

Routine clinical data such as demographics, performance status, disease status and treatment characteristics will be obtained at baseline and at each subsequent clinic visit when a research scan is obtained. This clinical data is all collected as part of standard of care for follow-up visits. It does not contain any study-specific procedures or information. Thus, non co-investigator MDs or NPs may perform the exam and collect the data in standard consultation and follow-up notes. The standard of care studies

including PET-CT, PFTs, and pathology reports will be obtained from the electronic medical record.

Radiation treatment for this protocol is exactly the same as it would be if the participant were not enrolled on the protocol. Radiation treatment data such as dose, dose per fraction, number of fractions and dose-volume histogram data will be obtained from the radiation oncology electronic archives.

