14.4 Timing of Collection of Data Elements

Scan data will be transferred to the cooperating labs for analysis within a month of the scan date. All other data will be transcribed from the clinical records within a month of the last protocol-related treatment/examination.

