14.5 Data Storage and Protection

Non-image data will be maintained in a web-based REDCap database developed specifically for this study. The REDCap database is password-protected. The PI will grant permission for specific study staff to have access to the portion of data pertinent to their role on the study.

Imaging data will be securely transferred to the [name] and [name] laboratories, where they will be stored in a password protected data archive housed behind the Partner's firewall. The MRI data to be transferred will be coded with the subject's study ID and not by name, to ensure confidentiality.

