15. STATISTICAL CONSIDERATIONS

15.1 Study Design/Endpoints

The primary objective of this study is to determine the feasibility of utilizing pulmonary DCE-MRI to assess changes from baseline in tumor perfusion during SBRT treatment

CONFIDENTIAL

This document is confidential. Do not disclose or use except as authorized.

(after 1 fraction of SBRT), and 1-2 weeks and 3-4 months after completion of SBRT treatment for stage I NSCLC. **Feasibility (success) is defined as successfully enrolling patients, processing the pulmonary DCE-MRI data, and observing an analyzable change in tumor perfusion between the pre-treatment DCE-MRI and any of the DCE-MRI scans during SBRT (after 1 fraction) or after completion of SBRT treatment. Analyzable change will be defined as a 20% change in tumor perfusion. A recent publication by Ng et al reported the rate of reproducibility of DCE-MRI parameters was between 10-20% (Ng, Raunig et al. 2010), and we have chosen the upper limit of this range to be conservative.**

A total of 20 participants with stage I NSCLC will be enrolled on this study, and a two-stage design will be used. Seven eligible participants in the first stage and 10 eligible participants in the second stage will be accrued. To allow for participants that are unable to complete scans and/or are ineligible to continue on the study, 3 additional participants will be accrued, so up to 8 participants in stage I and 12 participants in stage II will be accrued to this study. If at least 5 successes are observed among the 7 eligible participants in the first stage, up to an additional 12 participants (10 eligible) will be entered. If 14 or more successes are observed among the 17 eligible participants, utilizing pulmonary DCE-MRI to assess changes in tumor perfusion will be considered feasible for this group. With this design, there is a 90% probability of declaring the pilot study feasible if the true feasibility rate is 90%, and a 10% probability of declaring the DCE-MRI worthy of further study if the true feasibility rate is 65%. With 17 eligible participants, we have 90% power to detect a difference of 0.75 standard deviation in the change of tumor perfusion from baseline (prior to SBRT treatment) to post treatment (either right after SBRT treatment or 3-4 months after SBRT treatment) using a 0.1 level two-sided Wilcoxon signed-rank test.

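### The plan specifies no masking of time point or scan order for the tumor-perfusion readings that decide feasibility

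*Combined protocol and SAP*

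**What the plan says.** **Handling of the images.** Section 14.3 says "Images will be identified only by a study ID number" and that "The patient's identifying information (name, MR#, DOB) will be removed before the images are transferred". Section 14.5 gives the reason: "The MRI data to be transferred will be coded with the subject's study ID and not by name, to ensure confidentiality". The identifier belongs to the subject, not to the scan. Section 14.4 adds the timing: "Scan data will be transferred to the cooperating labs for analysis within a month of the scan date".

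**Use of the readings.** Section 15.1 requires, for each success, that the DCE-MRI data be processed and then "observing an analyzable change in tumor perfusion between the pre-treatment DCE-MRI and any of the DCE-MRI scans during SBRT (after 1 fraction") or after SBRT. It adds that "Analyzable change will be defined as a 20% change in tumor perfusion". The line sits at the top of a cited range, in which "the rate of reproducibility of DCE-MRI parameters was between 10-20" percent. Feasibility needs at least 5 successes in 7 participants, then at least 14 in 17. The stage I readings also decide which time points are kept in stage II.

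**Analysis method.** Section 7.2 describes a pharmacokinetic model fitted by a published pixel-wise method, "utilizing pixel-by pixel fitting". The plan does not say how the tumor region is set, when a fit is accepted, who reads the scans, or in what order.

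**The concern.** The primary endpoint is a measured value compared with a fixed line, together with a judgment that the data could be processed. Neither is protected by a rule that hides from the analyst which scan is baseline. All of a participant's comparisons use the same baseline scan, so one choice made on that scan affects all of them. There is no control arm in which the same reading tendency would appear and cancel. If the processing leaves any room for choice, even an unintended lean toward larger change would raise the success count. That count drives both decision rules and the choice of stage II time points.

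**Working it through.** **1. The plan's own figures.** With success probability p, the chance of declaring feasibility is

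P(p) = Σ(x = 5 to 7) C(7,x) p^x (1−p)^(7−x) × Pr{Bin(10,p) ≥ 14 − x}.

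- p = 0.90: 0.1240 × 0.7361 + 0.3720 × 0.9298 + 0.4783 × 0.9872 = 0.909 (stated 90%).
- p = 0.65: 0.2985 × 0.0860 + 0.1848 × 0.2616 + 0.0490 × 0.5138 = 0.099 (stated 10%).

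The design figures reproduce and are not in dispute.

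**2. Can scan order be seen on the stated schedule?** Section 7.1 places the baseline scan at Day 0 or earlier and the late scan at Day 90 to 120. With transfer within a month (14.4), baseline is due at the labs by about Day 30, at least 60 days before the late scan exists. A subject-level ID does not hide this. Order can be seen unless someone deliberately hides it, and the plan gives nobody that task.

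**3. Sensitivity without a measurement model.** Suppose the true rate is 65% and a share f of true failures is read as success. Then p = 0.65 + 0.35f. The value of f is an assumption.

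| f | p | P(p) |
|---|---|---|
| 0 | 0.650 | 9.9% |
| 5% | 0.6675 | 12.7% |
| 10% | 0.685 | 16.1% |
| 20% | 0.720 | 24.8% |
| 30% | 0.755 | 36.1% |

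**4. Sensitivity with a measurement model.** The assumptions are:

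- lognormal error with the same CV on every scan and s² = ln(1 + CV²);
- one shared baseline and three later scans;
- the same fall d on all three, where d is the true fall plus the reading shift;
- success if any ratio to baseline is ≤ 0.8 or ≥ 1.2.

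Section 15.1 does not define its 10-20% reproducibility statistic. Reading it as a per-scan CV is also an assumption. With e the baseline error, standard normal,

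q = 1 − E_e{[Φ(ln(1.2/(1−d))/s + e) − Φ(ln(0.8/(1−d))/s + e)]³},

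and the chance of declaring feasibility is P(q). Each cell shows shifts of 0 / 5 / 10 points toward a larger fall.

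| True fall | CV 10% | CV 15% | CV 20% |
|---|---|---|---|
| None | 0.01 / 0.01 / 0.15% | 10 / 11 / 16% | 58 / 59 / 63% |
| 10% | 0.15 / 4 / 36% | 16 / 30 / 56% | 63 / 71 / 81% |

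For a true fall of 10% at CV 10%, the underlying values of q are 44%, 59% and 76%.

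For a true fall of 30% with no shift, the chance is 99.5%, 96.7% and 96.7% at the three CVs. For 40% it is above 99.9% at CV 10% and 15%, and 99.9% at CV 20%.

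**The case against.** A reader might infer that the labs know which scan is baseline, and that someone draws the tumor by hand and chooses which fits to keep. The documents say neither. Sections 14.3 and 14.5 are privacy text, and a short list of removed identifiers does not specify what an analyst sees. Read literally, a label carrying only a study ID shows no time point. Section 7.2 describes pixel-wise fitting, which may leave little discretion. This part of the objection stands. The plan is silent, and visible scan order is an inference from the transfer schedule.

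The scenario figures can also be challenged, with reason. The shift is modeled simply as a larger fall in every participant on all three scans, and nothing in the documents supports 5 or 10 points. A true fall of 10% lies where the rule is sensitive. The 20% rule has no direction, so an expected fall is itself an assumption. Section 1.2 cites falls in a prostate series of 40% at 2 months and 75% at 6 months. Effects of that size would leave almost nothing for a reading shift to change. Those figures come from another tumor, however, and no earlier than 2 months, so they do not settle what the Day 2-3 and 1-2 week scans will show.

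Finally, this is a small pilot, its scans do not influence SBRT planning (Section 6.1), and masking the late scan will be imperfect. That limits the consequences, but it does not remove a low-cost protection for the study's only formal decision.

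**Conclusion.** The gap is real: the plan specifies no masking of time point or scan order, and no rule for the tumor region or for fit acceptance, behind a thresholded single-arm primary endpoint. The documents do not show that readings will be biased, and the size of any bias cannot be derived from them. The effect depends on the case:

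- It is largest when true change is modest and measurement error is at the lower or middle part of the cited range. With a 10% fall, a 10-point shift takes the chance of declaring feasibility from 0.15% to 36% at CV 10%, and from 16% to 56% at CV 15%.
- It is small with no true change: 0.01% to 0.15% at CV 10%, and 10% to 16% at CV 15%.
- It is negligible when true falls reach 30% or more.

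At CV 20%, noise alone already gives 58% with no true change, so a reading shift adds little there. These are assumed scenarios, not estimates. The point is a worthwhile, inexpensive improvement. It does not make the design invalid, and it changes no sample size.

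**What to change.** - **Section 14.3:** give each DCE-MRI scan its own random code, and remove scan date and time point before analysis. Name who holds the code.
- **Section 14.4:** have the labs process a participant's scans in random order once that participant's scans are complete, counting missed scans as closed. Adjust the transfer or analysis timing to match.
- **Sections 7.2 and 15.1:** write down how the tumor region is set and when a scan counts as processable. Lock the region, the processable call and the perfusion value before the code is broken.
- **Section 15.1, stage I:** break the code for stage I participants only after their values are locked, and before the review that chooses stage II time points.
- **Limitation to state:** the 3-4 month scan may still be recognisable from visible tumor or lung change.

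The cost is one coding step, a locked results table and later readings, since processing waits for each participant's last scan. No extra participant, scan or reader is needed, and the 5-of-7 and 14-of-17 rules stay as they are.
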